According to Adah et al, an RDT Reader is an automated device designed to enhance the accuracy and reliability of malaria diagnosis by interpreting RDT results through digital image analysis¹⁶. Functioning as a supplementary tool to traditional visual assessments, the RDT reader captures an image of the test strip and utilizes specialized software to analyze the presence or absence of malaria antigens, thereby reducing human error associated with manual interpretation. Examples of RDT readers are HealthPulse TestNow™, and the Deki Reader™ which are applications that guide users through the RDT process with step-by-step instructions, process control timers, and digital result interpretation. A field study in Côte d'Ivoire, Benin, and Nigeria using the Health Pulse RDT Reader demonstrated a 25% improvement in diagnostic accuracy compared to visual interpretation¹⁷. A study carried out by Karemere al evaluated the impact of Deki RDT readers on TPRs and data quality in 155 health facilities across two provinces in the Democratic Republic of Congo (DRC) from 2017 to 2019, comparing TPRs obtained from automated RDT readers, health DHIS2 data, and rainfall patterns to assess trends and reporting discrepancies¹⁸. Findings revealed that TPRs from automated readers were significantly lower on average than those recorded in HMIS data (22% TPR of reader compared to 69% in the HMIS), suggesting widespread overreporting of malaria cases. Additionally, TPRs recorded by automated readers aligned more closely with seasonal malaria transmission patterns, whereas HMIS-reported TPRs remained consistently high, indicating potential data manipulation. Similar results were observed in a 2022 follow-up study across three additional provinces (Kasai Central, Sud-Kivu, and Haut Katanga), where TPRs from facilities using Deki readers were 30-50% lower than those relying on HMIS-reported data

¹⁵ Karemere, J., et al. (2024). Evaluating the implementation of automated malaria rapid diagnostic test readers in health facilities in the DRC. American Journal of Tropical Medicine and Hygiene

¹⁶ https://www.auderenow.org/testnow.

¹⁷ BMGF & Audere. (2023). Health Pulse RDT Reader Study: Côte d'Ivoire, Benin, Nigeria. *Bill & Melinda Gates Foundation Report*.

¹⁸ Karemere, J., et al. (2024). Evaluating the implementation of automated malaria rapid diagnostic test readers in health facilities in the DRC. American Journal of Tropical Medicine and Hygiene, 112(1), 10-16

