nurses in charge of the participating health facilities after each count. The supervisors and the district health official will participate in the monthly count process, facilitated and chaired by the research team (at least for the first few months). Participants in the counting process will receive brief training on manual RDT result interpretation by the research team and use of the digital tool (a mobile app downloaded on a phone).

Sampling calculation

We hypothesize that the TPR recorded in the registers differs from the TPR found through the manual count and used the anticipated difference in our sample size calculations. We calculated sample size requirements based on a cluster randomized two-sample unpaired t-test for the comparison of two proportions using standard formulae (Hayes and Bennett, 1999). We fixed the Type 1 error at 5% and the power at 80%. Prior to the intervention we assume the TPR to be 65% in HFs and 95% in CHWs. We hypothesize that this, as a result of our intervention, will decrease to 40% in HFs and 50% in CHWs. We accordingly calculated separate sample sizes for HFs and CHWs based on the baseline and expected proportions. Since we will be sampling HFs and CHWs, we expect that there will be clustering effects in the populations that these Point Of Care serve. As such, we took clustering into account by applying a design effect based on the total population (i.e. total number of tests) that these POCs cover over six months (the assumed sampling time period) - using 2023 testing data for all HFs and CHWs in East region. We used an ICC of 0.05. Based on these assumptions and calculations, the maximum sample size required for HFs and CHWs respectively is 2121 and 1292 tests. We aim to sample from 16 HFs and 31 CHWs over a single district in the East region to control unknown confounders and differences in behavior/population between HFs and CHW catchment populations.

Tools for data collection

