In Depth Interviews with participants will be conducted in designated private spaces. If a private space is not available, an alternate location will be used to maintain confidentiality. Interviews will be audio recorded, transcribed verbatim in English language. Personal identifiers such as names and phone numbers will only be collected during the informed consent process and will not be recorded during interviews. The names of health facilities will be collected during data collection for identification purposes but will be excluded during data cleaning to ensure confidentiality.

To minimize risk of disclosure to others and discrimination or stigmatization, measures will be taken to avoid loss of confidentiality. A unique identification number will be assigned to all participants. Access to the completed study instruments and databases will be limited to the project manager, project lead, and data analysts. All data files will be password - protected.

Data analysis

1. Quantitative analysis

The primary outcome will be assessed with a chi-squared test to analyze whether the difference between reported TPR and counted TPR is significantly significant. This will include outcomes for an average across all surveyed points of care (POCs), disaggregated by HFs and CHWs, and compared between baseline (pre-intervention) and endline (after six months of the intervention).

We will further investigate the difference and change in TPR by constructing a mixed effects linear regression model with the POC-month as the unit of analysis and TPR as the outcome variable. The model will include a binary indicator to exhibit pre/post intervention (implementation of the RDT check), a binary variable to indicate intervention group (i.e. "reported" or "counted" TPR), a dummy variable to exhibit month since introduction of the intervention, and a random effect variable for POC type to account for clustering. 95% confidence intervals will be fit around the TPR per POC-month.

To determine whether changes in TPR were due to changes in provider behavior or changes to the DHIS2 data, the ratio of TPRs from the health facility register to the RDT cassettes will be plotted over the six months of the intervention and compared to the change in TPR reported from the DHIS2 data.

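### The supportive mixed model enters a pre/post indicator alongside month-since-introduction dummies that sum to it, so its pre/post coefficient has no fixed meaning and need not equal the change in reported TPR

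*Protocol*

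**What the plan says.** The primary outcome is tested by chi-squared. The protocol (Data analysis, 1. Quantitative analysis) then plans a further model, a "mixed effects linear regression model with the POC-month as the unit of analysis and TPR as the outcome variable", to study the difference and change in TPR. Its stated terms are:

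- pre/post: "The model will include a binary indicator to exhibit pre/post intervention";
- data source: "a binary variable to indicate intervention group (i.e. 'reported' or 'counted' TPR";
- month: "a dummy variable to exhibit month since introduction of the intervention";
- clustering: "a random effect variable for POC type to account for clustering".

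No reference month, constraint on the month effects or source-by-month interaction is given, and no coefficient is named as the one to be tested. The time contrast stated in the same section, for the chi-squared analysis, is baseline against endline after six months. Under Study Design, used cassettes are stored and collected during the study, so counted TPR has no baseline rows.

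**The concern.** A term called month since introduction separates post from pre by itself, so a pre/post indicator beside it is redundant. An analyst fitting the listed terms must drop a column or enter month as a number, and that unstated choice decides what the coefficient labelled pre/post measures.

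The month effects are also estimated from reported and counted rows together, so a movement in counted TPR alone can appear as a change after introduction. The protocol gives reason to expect such movement. Its aims look for counted and reported figures to converge over the six months, and its literature review says of the DRC reader study that "TPRs recorded by automated readers aligned more closely with seasonal malaria transmission patterns, whereas HMIS-reported TPRs remained consistently high".

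At stake is the protocol's only regression estimate of change in TPR, in a study whose findings go to the national programme and the Ministry.

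**Working it through.** **Inputs.** There are 16 HFs and 31 CHWs, 47 POCs in all (Study Design). HF TPR is assumed to be 65% at baseline, and of the later level the protocol says "We hypothesize that this, as a result of our intervention, will decrease to 40% in HFs and 50% in CHWs" (Sampling calculation). The required tests, 2121 and 1292, give 2121/(16×6) = 22 per HF-month and 1292/(31×6) = 7 per CHW-month. The plan states no figure for this model, so there is none to reproduce. Assumptions not in the protocol: six baseline months and the monthly pattern of counted TPR.

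**Step 1: rank.** For intercept, post, source and month dummies m1 to m6, post = m1 + ... + m6, giving 9 columns and rank 8. If the month term is read as one binary for time since introduction, it equals post (4 columns, rank 3). A trial fit of the mixed model with both terms returned no standard errors for post or any month term. Month as a number (0 before, 1 to 6 after) is full rank, but post is then a jump extrapolated to month 0.

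**Step 2: what the coefficient estimates.** Let gap_k = reported_k - counted_k, with one reported and one counted row per POC in each post month and reported rows only before. The source effect is fitted as minus the mean gap. Month k's effect against baseline is then

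(reported_k + counted_k)/2 - reported_pre + (mean gap)/2 = reported_k - reported_pre + (mean gap - gap_k)/2.

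With month r dropped, the pre/post coefficient is this expression at k = r.

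**Step 3: two examples.**

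*A. Reported flat at 65%; counted 30, 34, 38, 42, 46, 50%.* Gaps are 35, 31, 27, 23, 19, 15; mean 25.
- Month 1 dropped: 0 + (25 - 35)/2 = -5.0
- Month 6 dropped: 0 + (25 - 15)/2 = +5.0

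*B. Reported 65, 60, 55, 50, 45, 40%; counted constant at 40%.* Gaps are 25, 20, 15, 10, 5, 0; mean 12.5.
- Month 1 dropped: 0 + (12.5 - 25)/2 = -6.25
- Month 6 dropped: -25 + (12.5 - 0)/2 = -18.75

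| Points | Month 1 dropped | Month 6 dropped | Numeric month | Mean of six month contrasts | True six-month average change |
|---|---|---|---|---|---|
| A | -5.0 | +5.0 | -7.0 | 0.0 | 0.0 |
| B | -6.25 | -18.75 | -3.75 | -12.5 | -12.5 |

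In B, neither coefficient is even its own month's reported change, which is 0 in month 1 and -25 in month 6. The mean of the six contrasts is right because the gap terms cancel.

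**Step 4: rejection when reported TPR has not changed.** Simulation with 47 POCs, 22 or 7 tests per POC-month and six baseline months:

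- Counted TPR rising over ±5 points, dummy coding: 16% (ICC 0.05) to 34%.
- Rising over ±10 points, dummy coding: 73% (ICC 0.05) to 89%.
- ±10 points, numeric month: 99%.
- Month terms omitted: at most 0.3% by least squares at ICC 0.05 (±10 points), and 3% to 6% with POC intercepts and cluster-robust standard errors.
- Constant gap, month terms kept, least squares: 1% to 3%.
- With 36 baseline months, dummy coding rejects in 31% to 97% over the same ±5 and ±10 patterns.

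**Step 5: source of the false rejection.** Adding source-by-month to example A returns 0.0 whichever month is dropped. The grouping level is not the cause: for ±10 points, a mixed model with a random effect for POC type rejected in 107/150 runs with month terms and 0/150 without; with POC intercepts, 125/150 and 1/150.

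**The case against.** The strongest defence is that the fit itself is sound. Under dummy coding the fitted values do not depend on the dropped month, and the mean of the six month-against-baseline contrasts is already correct (0.0 and -12.5 above). On that view all that is missing is a reference level or a named contrast, which a SAP commonly supplies. The first part stands. The second does not fully answer the point: the protocol lists both terms and labels one as pre/post, so the model as stated is over-specified, not merely short of detail.

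Three further objections stand and limit the finding:

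- A reader might infer that the false rejections come from the redundant terms alone. They do not: under dummy coding they need month effects shared by both sources and a gap that varies by month.
- A reader might infer that the plan promises the average change over six months and that the model misses it. The protocol names no such target; its stated time contrast is baseline against endline. A month-6 estimate larger than the six-month average is not in itself an error.
- The rejection rates rest on assumptions. The literature review describes seasonality but gives no amplitude, and the outcome table compares with the same month in three previous years, so baseline length is open.

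A reader might also infer that the main result is compromised. The documents do not support that: the chi-squared test is primary and this model only investigates further.

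**Conclusion.** The model as listed is not identified under dummy coding, and this follows from algebra without any assumption about the data. Whatever column is dropped, the pre/post coefficient fails to give the change in reported TPR when the reported-counted gap varies by month, which the protocol itself anticipates. In the worked cases it ranges from -5.0 to +5.0 points when the true change is 0, and from -6.25 to -18.75 when the true six-month average is -12.5.

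The false-rejection rates (about 16% to 34% for ±5 points and 73% to 89% for ±10 points, with dummy coding and six baseline months) illustrate the size of the problem and are not predictions. They depend on assumed amplitude, baseline length and clustering. With a constant gap there is no material false rejection at six baseline months; with a source-by-month term the coefficient is the reported change for the reference month only. The primary test stands. The correction is still worth making before analysis, because it alters what the only regression estimate of change would report.

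**What to change.** Do not enter the pre/post indicator and the month-since-introduction terms together. Estimate change from reported TPR rows only, in one of two ways:

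- the pre/post indicator without month-since-introduction terms; or
- six month dummies against baseline in place of the indicator.

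Name in advance the contrast to be reported with its confidence interval: the average of the six months, or month 6 against baseline if it is to match the stated baseline-endline comparison. Examine reported minus counted TPR by month in a separate within-month comparison, so that convergence over time is still shown.

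The cost is one sentence of wording and a second simple model; no new data are needed. One limitation remains: neither version adjusts for season in reported TPR unless calendar-month terms shared by the pre and post months are added.

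### The mixed model's only clustering term is a random effect for POC type, which has two levels, so repeated rows from the same point of care are treated as independent

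*Protocol*

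**What the plan says.** The Protocol, Data analysis, 1. Quantitative analysis, plans "constructing a mixed effects linear regression model with the POC-month as the unit of analysis and TPR as the outcome variable". The listed terms are a pre/post indicator, an indicator for reported versus counted TPR, a month-since-introduction dummy, and "a random effect variable for POC type to account for clustering". The Protocol states no random effect for the individual POC, no repeated-measures covariance and no cluster-robust variance.

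The same section shows what type means. The chi-squared results are to be given as "an average across all surveyed points of care (POCs), disaggregated by HFs and CHWs", so type has two values.

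The Sampling calculation section puts clustering elsewhere, at the individual facility or CHW: "we took clustering into account by applying a design effect based on the total population", with an ICC of 0.05. The number of units is also stated there: "We aim to sample from 16 HFs and 31 CHWs over a single district in the East region".

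**The concern.** The sample size was inflated for clustering within individual points of care, but the model recognises only two clusters. This has two consequences.

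- A variance component fitted to two levels is nearly unidentified. HF versus CHW is a known contrast of interest and belongs in the model as a fixed effect.
- Given type and the fixed effects, every row from one POC is treated as independent of its other rows. The model ignores both the POC's own TPR level and any POC-specific gap or change.

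These two omissions pull in opposite directions. Ignoring the POC's level makes SEs for within-POC contrasts too wide. Ignoring POC-specific gaps or changes makes them too narrow. The team cannot know beforehand which dominates. Heterogeneity is plausible, since the background section attributes high positivity to provider misreading and incentive-driven overreporting, which need not be equal across providers.

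**Working it through.** The plan gives no figure for this model to reproduce. Its computed sample sizes, 2121 and 1292 tests, rest on a mean cluster size that is not stated. They cannot be checked, and the point does not depend on them.

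**1. Rows and levels.** 16 + 31 = 47 POCs. Post-introduction rows: 47 × 6 months × 2 sources = 564. With six pre-intervention months of reported TPR (an assumption), add 47 × 6 = 282, giving 846 rows over two random-effect levels.

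**2. Inputs.** The documents give no SDs, so these are assumptions, scaled to the protocol where possible.
- Between-POC SD σu = 0.10. For comparison, ICC 0.05 implies √(0.05 × 0.65 × 0.35) = 0.107 at the HF baseline of 65% and √(0.05 × 0.95 × 0.05) = 0.049 at the CHW baseline of 95%.
- Residual SD σe = 0.08. Tests per POC-month are 2121/(16 × 6) = 22.1 for HFs and 1292/(31 × 6) = 6.9 for CHWs. Binomial noise is then √(0.95 × 0.2275/22.1) = 0.099 and √(0.95 × 0.0475/6.9) = 0.081.
- SD of POC-specific gaps, σg, from 0 to 0.15. SD of POC-specific pre/post changes, σq, from 0 to 0.10 (0.15 in step 4).

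**3. Reported-counted gap.** Two thirds of rows are post-introduction and one third are counted, so the type-only model sees residual variance s² = σu² + σe² + (2/3)σq² + (1/3)σg².
- SE claimed by the model: √(2s²/282).
- True SE: √[(σg² + 2σe²/6)/47].

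The table sets these beside a simulation with no true mean gap (400 data sets per row; type entered as fixed, which is equivalent for contrasts within type).

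| σg | σq | Model SE, formula | True SE, formula | Model SE, simulated | Actual SD, simulated | Rejection, type only | Rejection, clustered on POC |
|---|---|---|---|---|---|---|---|
| 0 | 0 | 0.0108 | 0.0067 | 0.0106 | 0.0067 | 0% | 6.5% |
| 0.05 | 0.05 | 0.0116 | 0.0099 | 0.0114 | 0.0098 | 2.2% | 3.5% |
| 0.10 | 0.10 | 0.0137 | 0.0161 | 0.0134 | 0.0172 | 12.2% | 6.0% |
| 0.15 | 0.10 | 0.0147 | 0.0229 | 0.0145 | 0.0235 | 24.0% | 4.8% |

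Equating the two formulas gives the crossover σg² = (3/8)σu² + (1/4)σq². With σu = 0.10 and σq = 0, that is σg = 0.061. Below about 6 points of between-POC variation in the gap the test is too conservative; above it, too liberal.

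**4. Pre/post change.** Using reported rows only, s² = σu² + σe² + σq²/2, and the two SEs have the same form with σq in place of σg.
- σq = 0: model 0.0108, true 0.0067.
- σq = 0.10: model 0.0123, true 0.0161, so rejection is 2Φ(−1.96 × 0.767) = 13%.
- σq = 0.15: model 0.0140, true 0.0229, so rejection is 23%.

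With the counted rows also in the model the test is more conservative. Simulated rejection was 0% with no heterogeneity and 6.2% at σq = σg = 0.10.

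**5. Sensitivity to set-up.** Take 22 and 7 tests per POC-month, ICC 0.05 and six months on each side.
- When POCs differ in level only, the pre/post SE was 0.0131 against a true 0.0101 (1.3% rejection).
- Change SDs of 10 and 15 points gave 11% and 28% false positives. Other choices of rows and SDs gave 5-12% and 14.5-24%.
- For the gap, the SE was 1.9 to 2.3 times too wide at gap SD 5 points. At SD 20 points there were 19-30% false positives.
- Clustering on the POC gave about 2.5-8% throughout.

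**6. TPR level.** With type as fixed, the SE of the HF mean was 0.010-0.013 against an actual SD of 0.025-0.042, and rejection was 46-56%. With type as a random effect, as written, the error reverses. One fitted data set gave an intercept SE of 0.078, and another a 95% interval for mean TPR of 0.51-0.97.

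**7. A POC random intercept alone.** At σg = σq = 0.10, over 100 simulated data sets, the mean SE of the gap was 0.0135 with random type, 0.0088 with a random POC intercept only, and 0.0160 with POC-specific source and period effects. The formula value is 0.0161. Rejection was 8%, 23% and 2%.

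**The case against.** Four points can be made for the plan.

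- **The model is supporting.** The primary outcome goes to a chi-squared test, and this is an observational pilot. That is true and limits the reach of the error. But the chi-squared test as stated makes no allowance for clustering, so this model is the only stated analysis that claims to.
- **The planned effects are large.** The protocol hypothesises falls of 25 points (HF) and 45 points (CHW). Even with POC-specific SDs of 20 points, heterogeneity gives SEs of 20/√16 = 5 points and 20/√31 = 3.6 points, so these effects are 5 and about 12.5 SEs. This stands for detecting effects of that size. It does not cover the aim of seeing whether the discrepancy vanishes over the six months. There the gap is near zero and the accuracy of the interval decides the reading.
- **The inflated error rates rest on assumed SDs.** This also stands. With the protocol's ICC alone the contrasts are conservative. No single error rate can be quoted, only a range.
- **Type may be a slip for POC.** Possible, given the stated purpose of the term. But an analyst would fit what is written, and a later SAP would inherit it. Correcting that one word would also leave the gap SE too small if POCs differ in their gaps (step 7 of the working).

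**Conclusion.** Wrong as written. The Protocol names a clustering term and places it at a two-level factor, when its own sample-size section puts clustering at the 47 individual POCs. This is a stated rule at the wrong level, so it is not a detail left to the SAP.

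The standard errors are wrong rather than simply too narrow. Under the assumed SDs, the model SE for the reported-counted gap runs from 1.6 times too large (no variation in the gap) to about 0.6 of the true value (gap SD 15 points, 24% rejection). The pre/post contrast follows the same pattern, with a size that depends on which rows enter the model. Intervals for TPR levels are far too narrow if type is fixed, and dominated by a two-unit variance if it is random. The direction and size in the real data depend on between-POC variation that the documents do not give. The need for POC-level terms does not depend on it.

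**What to change.** In Data analysis, 1. Quantitative analysis, replace the random effect for POC type with:

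- a random intercept for the individual POC, plus POC-specific random effects for source (reported or counted) and for pre/post; or, as an alternative, standard errors clustered on the POC with a small-sample correction;
- POC type (HF or CHW) as a fixed effect, with its interaction with source.

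A POC random intercept without the POC-specific source and period effects is not enough. The cost is one sentence in the analysis section, settled before analysis, with no extra data or staff.

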Malaria remains a leading public health challenge in Cameroon, with diagnostic accuracy and data quality among the key barriers to effective case management⁴. The country relies heavily on rapid diagnostic tests (RDTs), with 69% of patients tested using RDTs in 2023⁵. However, very high Test Positivity Rates (TPRs) and supply chain inefficiencies raise concerns about the accuracy of reported malaria cases in Cameroon⁶: Providers may not interpret the test accurately or may report negative RDTs as positive. This could lead to inflated case counts and incidence which distort trends and contribute to observed lack of progress in reducing malaria burden. In addition, administering these patients antimalarials may not address the true cause of illness which can increase the risk to patients for morbidity and mortality. Finally, irrational ACT use may contribute to stockouts as well as wastage and increased risk of developing antimalaria resistance.

Data from the District Health Information System (DHIS2) show that TPR varies widely across Cameroon, with the Southwest reporting rates as high as 89% among public sector health workers, while some regions reporting in the lower 60% range. The Annual Blood Examination Rate (ABER) is highest in the East, Adamawa and Far North regions, ranging between 15-26% (including active testing). The average TPR among Community Health Workers (CHWs) is 83%, significantly higher than in health facilities, with minimal variation between age groups. While it is plausible that CHWs, as first-line responders, test only febrile patients with a high likelihood of malaria, qualitative data suggest that other factors may be influencing these high positivity rates. Key Informant Interviews (KIIs) with malaria experts in Cameroon conducted by CHAI in 2023 for example indicate that financial incentives tied to reporting positive cases could be a factor, leading to potential overreporting of malaria cases⁷.

The high TPR has led to questions around the accuracy of reporting the test results by health worker (HW) and community health workers (CHW). Previous efforts in other low- and middle-income countries have shown discrepancies between reported and 'true' TPRs (i.e., using

¹ WHO Malaria Guidelines 2023

² A review of the WHO malaria rapid diagnostic test product testing program (2008–2018): performance, procurement and policy. Jane Cunningham, 2019.

³ World Malaria Report, WHO, 2024.

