Data will be collected through a review of routine health records, one survey and in depth interviews to assess the introduction of the counting on performance, diagnostic accuracy, and stock management outcomes. The routine health records include the registers, which will be filled by health care workers (health facility and CHWs), and the DHIS2, metadata on test results, RDT and ACT consumption data and timestamps for each test. During the data validation meetings, the aggregated results of the manual and digital count and the health records will be recorded and stored in a cloud-based system. For the digital count, we will use a customized Audere 'Healthpulse' Android mobile app on a phone provided by the research. The user is instructed to open the app and prompted to take a picture of the RDT result window. The Audere app is trained to interpret and provide the result of the RDT picture to the end user. The aggregated digital and manual count will be compared and any discrepancies will be reviewed and resolved by the supervisor, the district health official and the research team.

A survey will be conducted among the participating health workers on their perceptions of malaria RDTs. In depth interviews will be conducted with all stakeholders involved in the data

validation meetings to explore feasibility of the validation meetings post study. The research team will also collect data on the financial and human resources required to conduct the RDT counts.

Study Outcome Measures

The primary outcome of the study will be the RDT volume and TPRs obtained from the manual count compared with the RDT counts TPRs recorded in the HMIS, health facility registers, and CHW records. This will provide insights into potential discrepancies in malaria diagnosis and reporting accuracy.

Specific outcomes will include the following:

S/N	Type of Outcomes	Outcome	Methods of measurement
1	Primary	The volume and proportion of RDT results reported as positive	On a monthly basis, RDT counts and RDT positives recorded through the manual count will be compared to RDT count and TPR recorded in the registers (by health facility and CHWs attached to that facility) and what was recorded in the DHS2 for that facility and for the CHWs attached to that facility

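### The register-to-cassette TPR ratio shifts with true positivity even when misreporting is constant, and the planned DHIS2 comparison only partly resolves this

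*Protocol*

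**What the plan says.** Protocol, Data analysis, 1. Quantitative analysis, gives this analysis an explicit purpose: "To determine whether changes in TPR were due to changes in provider behavior or changes to the DHIS2 data". The method is that "the ratio of TPRs from the health facility register to the RDT cassettes will be plotted over the six months of the intervention", and that it is "compared to the change in TPR reported from the DHIS2 data". Nothing in the sentence adjusts for true positivity or season, and only the facility register is named.

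Other parts of the protocol bear on this:

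- The background section gives the suspected mechanism: "Providers may not interpret the test accurately or may report negative RDTs as positive".
- The literature review (3. Interventions to improve Malaria Diagnosis) reports that reader-based TPR in another country "aligned more closely with seasonal malaria transmission patterns", while HMIS TPR stayed high.
- Tools for data collection describes registers "which will be filled by health care workers (health facility and CHWs").
- Sampling calculation: "Prior to the intervention we assume the TPR to be 65% in HFs and 95% in CHWs", and the hypothesis is that these "will decrease to 40% in HFs and 50% in CHWs".

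**The concern.** The ratio's denominator is the TPR on the cassettes. That quantity can change over six months because transmission changes, not because anyone records differently. If negatives are written up as positives, the number of negatives available to be misrecorded shrinks as true positivity rises, so the ratio falls by itself. It rises by itself when positivity drops.

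The sentence allows only two explanations, provider behaviour or DHIS2 data, and true positivity is neither. A seasonal shift can therefore be credited to one of them, and a real improvement in recording can be hidden. The findings are meant for the national programme and for policy briefs on possible scale-up, so a wrong attribution would matter.

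Two gaps add to this. CHW registers are left out of this analysis, although the protocol assumes the larger change among CHWs. And DHIS2 is compared with the ratio, not with the register, so the step from register to DHIS2 is not isolated.

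**Working it through.** The protocol states no figure for this analysis, so there is none to reproduce.

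**Inputs.** Facility TPR of 65% before and 40% expected under the intervention; CHW TPR of 95% and 50% (Sampling calculation). *Assumptions:* the first of each pair is the register TPR and the second the cassette TPR; true TPR c ranges over 30% to 60%. The protocol gives no seasonal range for the district.

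**Formula.** With a share p of negatives recorded as positive:

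- Register TPR = c + p(1-c)
- Ratio = 1 + p(1-c)/c
- p = (register TPR - c)/(1-c)

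**Calibration.** Facilities: p = (0.65-0.40)/0.60 = 0.417. CHWs: p = (0.95-0.50)/0.50 = 0.90.

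**Ratio with p held constant:**

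| c | Facility register TPR | Facility ratio | CHW ratio |
|---|---|---|---|
| 30% | 59.2% | 1.97 | 3.10 |
| 40% | 65.0% | 1.63 | 2.35 |
| 50% | 70.8% | 1.42 | 1.90 |
| 60% | 76.7% | 1.28 | 1.60 |

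Allowing 2% or 5% of positives to be recorded as negative, with p recalibrated, leaves the facility ratio at 1.98 to 2.00 for c = 30% and 1.27 to 1.25 for c = 60%.

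**Does the DHIS2 comparison rescue it?** Suppose DHIS2 copies the facility register exactly:

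| Scenario | c | p | DHIS2 TPR | Ratio |
|---|---|---|---|---|
| A. c rises, behaviour constant | 40% to 60% | 0.417 | 65.0% to 76.7% | 1.63 to 1.28 |
| B. c constant, behaviour improves | 40% | 0.417 to 0.25 | 65.0% to 55.0% | 1.63 to 1.38 |
| C. c falls, behaviour constant | 60% to 40% | 0.417 | 76.7% to 65.0% | 1.28 to 1.63 |
| D. c falls, behaviour improves | 60% to 40% | 0.417 to 0.25 | 76.7% to 55.0% | 1.28 to 1.38 |

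(In B and D, the final register TPR is 0.40 + 0.25 × 0.60 = 0.55, and 0.55/0.40 = 1.375.)

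A and B differ in direction: DHIS2 TPR rises in A and falls in B. C and D do not differ: in both, the ratio rises and DHIS2 TPR falls. Under the sentence's two-way choice, a falling DHIS2 TPR without a falling ratio points to DHIS2 data. Yet DHIS2 practice is unchanged in both, and in D providers improved by 40% (0.417 to 0.25).

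**Checking a replacement.** Take 100 tests, 40 truly positive, with 25 of the 60 negatives recorded as positive, so the register shows 65 positives. Three candidates for the recording step, with all cassettes kept and then with 20 negative cassettes discarded:

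- (register positives - cassette positives)/cassette negatives: 25/60 = 0.417, then 25/40 = 0.625.
- (register TPR - cassette TPR)/(1 - cassette TPR): 0.25/0.60 = 0.417, then cassette TPR is 40/80 = 0.50 and the result is 0.15/0.50 = 0.30.
- (register positives - cassette positives)/(register total - cassette positives): 25/60 = 0.417, and still 25/60 = 0.417.

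Only the third is unaffected by lost negatives. Lost positives still inflate it: with 10 missing it becomes (65-30)/(100-30) = 0.50.

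**Limit of any such index.** If register TPR stayed flat at 65% whatever the season, the index would run from (0.65-0.30)/0.70 = 0.50 at c = 30% to (0.65-0.60)/0.40 = 0.125 at c = 60%.

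**The case against.** A reader might infer that the ratio can never separate provider behaviour from other causes. The documents do not support that. The protocol reads the ratio beside DHIS2 TPR, and in scenario A the two move in opposite directions, which distinguishes a rise in transmission from improvement at stable transmission. A ratio of exactly 1 also means no net over-reporting at any true TPR. Both points stand, but they do not cover falling transmission or simultaneous change.

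A reader might also infer that CHWs, or the DHIS2 and register comparisons, are missing from the plan as a whole. They are not. The outcome table compares manual counts monthly with both registers and DHIS2, for each facility and its attached CHWs, and the chi-squared test is disaggregated by facilities and CHWs. The omission is confined to this attribution analysis. Same-month comparisons with the three previous years and with surrounding districts are planned too, but they use DHIS2 TPR without cassette counts and so cannot correct the ratio.

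The constant-share model is an idealisation. The literature review's account of a persistently high HMIS TPR fits a flat reported rate better. Under that pattern the ratio still drifts (0.65/0.30 = 2.17 against 0.65/0.60 = 1.08), but so does the replacement index, so no single index is proof against season.

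Finally, this is a descriptive plot without a decision rule, in a pilot, and an unseen SAP could add lines or panels. That limits the weight. But the protocol itself chose the metric and said what it is to determine.

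**Conclusion.** The concern holds in a limited form. Under the protocol's own suspected mechanism, the ratio depends on true positivity as well as on behaviour. For facilities it moves from 1.63 to 1.28 as c goes from 40% to 60% with nothing else changed. Read beside DHIS2 TPR, it remains ambiguous when c falls or when c and p change together, and can worsen (1.28 to 1.38) while recording really improves.

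The direction follows from the algebra for any constant p above zero. The size rests on two assumptions: that the expected 40% stands for the cassette TPR, and that true TPR varies within 30% to 60%. A reader might take 1.97 to 1.28 as the drift expected in this district; the protocol gives no seasonal range from which to say so.

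Leaving CHW registers out and not setting DHIS2 against the register are plain from the sentence. The analysis should be changed, but it can be repaired with data already planned for collection.

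**What to change.** Replace the ratio sentence with an analysis done separately for facilities and CHWs:

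1. Plot monthly cassette, register and DHIS2 TPR as three lines.
2. Recording step: (register positives - cassette positives)/(register total - cassette positives), the net share of negatives recorded as positive.
3. Reporting step: DHIS2 TPR minus register TPR.
4. Show counted against registered RDT volume beside these to flag cassette loss, since lost positive cassettes inflate the recording measure.
5. State that the recording measure is free of season only if the misreporting share is constant, so attribution is read from all the lines together and not from one index.

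The cost is a rewritten paragraph, a little more analysis work and a few more plotted lines. No new data are needed, because all three sources are already to be collected for facilities and CHWs.
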